#### 10.1.1. Incidence of Adverse Events

The incidence of AE table will include only one occurrence of a PT per patient. If a patient reports the same PT multiple times, then that PT will only be incremented by one since patient counts will be presented. As with the PT, if a patient reports multiple AEs within the same SOC, then that SOC will only be incremented by one since patient counts will be presented. For tables showing incidence by SOC and PT, PTs will be sorted within SOC in descending order of incidence in the total RPC1063 group. For tables showing incidence by PT only, the PTs will be sorted in descending incidence in the total RPC1063 group.

The incidence of all treatment-emergent AEs will be presented by SOC and PT and separately by PT only. In addition, the incidence of all treatment-emergent AEs that occur in  $\geq 2\%$  of the total RPC1063 group will be presented by PT.

All AEs will be presented in a listing.

### 10.1.2. Relationship of Adverse Events to Investigational Product

A summary of AEs by relationship to study drug will be presented in a table by incidence of occurrence. The relationships will be collected as the possibility that study drug caused the event. The possible relationships are "Unrelated", "Unlikely", "Possible", "Probable" and "Related". A treatment-related AE is an AE with any relation to study drug other than "Unrelated" or "Unlikely". In the AE relationship table, if a patient reports multiple occurrences of the same AE, only the most closely related occurrence will be presented. Adverse events (AE) that are missing relationship will be presented in the summary table as "Probable" but will be presented in the data listing with a missing relationship.

### **10.1.3.** Severity of Adverse Event

A summary of AEs by severity will be presented in a table. Adverse events will be classified by severity (mild, moderate and severe). In the AE severity table, if a patient reported multiple occurrences of the same AE, only the most severe will be presented. Adverse events that are missing severity will be presented on tables as "Severe" but will be presented in the data listing with a missing severity.

#### 10.1.4. Serious Adverse Events

The seriousness of an AE should be assessed by the Investigator independently from the severity of the AE. A serious adverse event (SAE) is defined as any untoward medical occurrence that at any dose results in death, is life-threatening, requires inpatient hospitalization or prolongation of existing inpatient hospitalization, or results in significant disability/incapacity.

Important medical events that may not result in death, be life-threatening, or require hospitalization may be considered SAEs when, based upon medical judgment, they may jeopardize the patient and may require medical or surgical intervention to prevent one of the outcomes listed above.

The incidence of SAEs will be presented in a table. The incidence of treatment-related SAEs will also be presented in a table. A treatment-related SAE is a SAE with any relation to study drug other than "Unrelated" or "Unlikely". The table of SAEs will include only one occurrence of a PT per patient. If a patient reports the same SAE multiple times, then that PT will only be incremented by one since patient counts will be presented. As with the PT, if a patient reports multiple SAEs within the same SOC, then that SOC will only be incremented by one since patient counts will be presented. SAEs will also be listed separately.

#### **10.1.5.** Adverse Events Leading to Treatment Discontinuation

All AEs collected with an investigational product action taken as "Permanently discontinued" will be summarized in a table and presented in a listing.

#### 10.1.6. Death

All patient deaths during this study will be collected and presented in a listing. The information that is presented includes date of death, days on study, cause of death, and relationship of death to study drug.

#### **10.1.7.** Adverse Events of Special Interest

Target AEs of special interest will be closely monitored in the study. These AEs include infections, malignancies, cardiac (bradycardia and heart conduction abnormalities), pulmonary function (decline in FEV1, FVC, and DLCO measurements), ophthalmic (macular edema), hepatic (LFT elevations), and dermatological (cutaneous malignancy) abnormalities. These AEs will be summarized in tables and presented in a listing.

### 10.2. Clinical Laboratory Evaluations

Laboratory assessments will be performed by a central laboratory. All summaries will be based on the SI units provided by the central lab.

Summary tables including actual values and change from Baseline values will be presented for clinical laboratory tests with numeric values by treatment group.

Laboratory data will be summarized using shift tables where appropriate. Each patient's hematology and blood chemistry values will be flagged as "low", "normal", or "high" relative to the normal ranges of the central laboratory or as "unknown" if no result is available. Each patient's urinalysis values will be flagged as "positive", "negative", or if no value is available, "unknown".

### 10.2.1. Hematology

The following laboratory tests will be included in hematology summary tables of actual value and change from Baseline: red blood cell (RBC) count, total and differential WBC count (basophils, eosinophils, lymphocytes, monocytes, and neutrophils), platelet count, hemoglobin, hematocrit, mean corpuscular volume (MCV), mean corpuscular hemoglobin (MCH), and mean corpuscular hemoglobin concentration (MCHC). Total and differential WBC counts will be blinded after the onset of study treatment. A listing will present abnormal hematology values (except for lymphocytes between 200 cells/uL and the lower limit of normal) for all patients.

Patients with abnormalities in hematology assessments, defined as absolute lymphocyte count (ALC) < 200 cells/uL, absolute neutrophil count (ANC) < 500 cells/uL, ANC < 1000 cells/uL, and total WBC > 20,000 cells/uL will be summarized by treatment group.

Actual value, change, and percent change in ALC will plotted in line graphs over time showing the means and standard errors (SE).

#### 10.2.2. Blood Chemistry

The following laboratory tests will be included for blood chemistry summary tables at the screening visit: sodium, potassium, chloride, calcium, magnesium, phosphate, blood urea nitrogen, random glucose, hemoglobin A1c, albumin, alkaline phosphatase, creatinine, SGPT/ALT, SGOT/AST, gamma glutamyltransferase (GGT), amylase, total bilirubin, conjugated bilirubin, total cholesterol, triglycerides, HDL and LDL. For all other visits, which will be subject to change from Baseline reporting, the tests will include blood urea nitrogen, hemoglobin A1c, albumin, alkaline phosphatase, creatinine, SGPT/ALT, SGOT/AST, GGT, amylase, total bilirubin, and conjugated bilirubin.

A listing will present abnormal chemistry values for all patients.

The incidence of patients with abnormalities in Liver Function Tests (SGPT/ALT, SGOT/AST, and GGT) will be summarized overall and at each visit for each treatment group for the following categories:

- > 1 x upper limit of normal (ULN)
- $> 2 \times ULN$
- $> 3 \times ULN$
- $\geq 4 \times ULN$
- $\geq 5 \times ULN$

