#### **Screening Period**

During the screening period, the following procedures will be performed:

- Obtain patient's informed consent
- Inclusion/exclusion criteria
- Complete medical history
- Blood/urine sampling for the following laboratory tests:
  - Hematology: red blood cell (RBC) count, total and differential WBC count (basophils, eosinophils, lymphocytes, monocytes, and neutrophils), platelet count, hemoglobin, hematocrit, mean corpuscular volume (MCV), mean corpuscular hemoglobin (MCH), and mean corpuscular hemoglobin concentration (MCHC)
  - Blood chemistry: sodium, potassium, chloride, calcium, magnesium, phosphate, blood urea nitrogen, random glucose, albumin, alkaline phosphatase, creatinine, SGPT/ALT, SGOT/AST, gamma glutamyltransferase (GGT), amylase, total bilirubin, conjugated bilirubin, hemoglobin A1c. Abnormal laboratory parameters inconsistent with clinical presentation of MS or suspicious of underlying medical condition should be repeated for accuracy.
  - Urinalysis: leukocytes, specific gravity, bilirubin, blood, glucose, ketones, pH, protein, and urobilinogen
  - Serum beta-human chorionic gonadotrophin (β-hCG) (women of childbearing potential only)
  - Coagulation panel: prothrombin time (PT) and partial thromboplastin time (PTT)
  - Sensitive thyroid stimulating hormone (sTSH)
  - Viral serology: HIV antibodies, anti-hepatitis A virus IgM, HBsAg and HBcAg IgM, anti-HCV IgG or IgM. In addition, patients must have documentation of positive VZV IgG antibody status. Patients who are negative for VZV IgG antibodies at screening can undergo vaccination and be enrolled 30 days after appropriate VZV vaccination has been completed. Patients testing positive for HIV or for serological markers of acute or chronic hepatitis A, B, or C will be

excluded from the study unless they are indicative of prior hepatitis B vaccination or cured hepatitis A or B and accompanied by normal liver transaminase values.

- Syphilis RPR. Patients must have a negative result to be enrolled.

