#### 10.3.1. Visit 1 (Baseline/Month 1)

Eligible patients will be randomized to treatment group on Visit 1.

The following assessments will be performed at the Visit 1 (Baseline/Month 1):

- Review of inclusion/exclusion criteria
- An interim medical history will be performed to complete the screening medical history. Medical events that occur between screening and first dose will be recorded as medical history
- Blood/urine sampling for the following laboratory tests:
  - Hematology: RBC count, total and differential WBC count (basophils, eosinophils, lymphocytes, monocytes, and neutrophils), platelet count, hemoglobin, hematocrit, MCV, MCH, and MCHC
     Note: All total WBC and differential WBC counts will be blinded during the study.
  - Blood chemistry: sodium, potassium, chloride, calcium, magnesium, phosphate, blood urea nitrogen, random glucose, albumin, alkaline phosphatase, creatinine, SGPT/ALT, SGOT/AST, GGT, amylase, total bilirubin, conjugated bilirubin, hemoglobin A1c, and total cholesterol, triglycerides, high-density lipoprotein (HDL), and low-density lipoprotein (LDL).
  - Urinalysis: leukocytes, specific gravity, bilirubin, blood, glucose, ketones, pH, protein, and urobilinogen.
  - Urine beta-hCG (females of childbearing potential only). If the urine pregnancy test is positive, do not dose and confirm with a serum pregnancy test.
  - Standard PK sampling: PK sample is to be taken prior to dose administration
- Weight
- Vital signs: body temperature, blood pressure and heart rate. The special first dose monitoring procedures must be performed (see below and Guidelines for Monitoring Patients Taking Their First Dose in Section 10.2.1.1)
- 12-lead ECG. The special first dose monitoring procedures must be performed (see below and Guidelines for Monitoring Patients Taking Their First Dose in Section 10.2.1.1)
- Randomization
- Dispense study drug (with titration kit) and patient diary, and administer first dose of study drug at the site
- MSFC AND LCLA
- MSQOL-54

Efficacy and Safety of Oral RPC1063 in RMS Patients

01 October 2014 Version 4.0

- Suicidality assessment using the C-SSRS
- Record concomitant therapy
- Record AEs/SAEs

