#### 10.3.10. Visit 10 (Month 24/Week 104 $\pm$ 5 days)

Patients are expected to remain in Part B for 24 months.

The following assessments will be performed at Visit 10 (Month 24):

- Blood/urine sampling for the following laboratory tests:
  - Hematology: RBC count, total and differential WBC count (basophils, eosinophils, lymphocytes, monocytes, and neutrophils), platelet count, hemoglobin, hematocrit, MCV, MCH, and MCHC
     Note: All total WBC and differential WBC counts will be blinded during the study.
  - Blood chemistry: sodium, potassium, chloride, calcium, magnesium, phosphate, blood urea nitrogen, random glucose, albumin, alkaline phosphatase, creatinine, SGPT/ALT, SGOT/AST, GGT, amylase, total bilirubin, conjugated bilirubin, hemoglobin A1c, and total cholesterol, triglycerides, HDL and LDL. Abnormal laboratory parameters inconsistent with clinical presentation of MS or suspicious of underlying medical condition should be repeated for accuracy. If an increase of amylase above the clinically notable value (≥ 300 U/L) is observed at any post randomization visit, lipase should be tested to determine the origin of elevated amylase (pancreatic versus extra pancreatic)
  - Urinalysis: leukocytes, specific gravity, bilirubin, blood, glucose, ketones, pH, protein, and urobilinogen
  - Urine beta-hCG (females of childbearing potential only). If the urine pregnancy test is positive, do not dose and confirm with a serum pregnancy test.
  - Coagulation panel: PT and PTT
  - sTSH

- Standard PK sampling: PK samples are to be taken 2 to 6 hours following administration
- Complete physical examination: including evaluation of heart, lung, head and neck, abdominal, neurological, skin, and extremities
- Weight
- Vital signs: body temperature, blood pressure and heart rate
- 12-lead ECG
- If patients will continue on treatment, dispense study drug and patient diary
- Review study drug accountability and compliance
- Brain MRI
- EDSS and neurological examination
- MSFC AND LCLA
- MSQOL-54
- Pulmonary function tests including FEV1 and FVC measurements, and DLCO
- OCT evaluation
- Dermatological examination
- Suicidality assessment using the C-SSRS
- Record concomitant therapy
- Record AEs/SAEs

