#### • Routine safety laboratory tests:

- Hematology RBC count, total and differential WBC count (basophils, eosinophils, lymphocytes, monocytes, and neutrophils), platelet count, hemoglobin, hematocrit, MCV, MCH, and MCHC. Total WBC and all differential WBC counts will be blinded information for the treating investigator after the onset of study treatment.
- Chemistry sodium, potassium, chloride, calcium, magnesium, phosphate, blood urea nitrogen, random glucose, hemoglobin A1c, albumin, alkaline phosphatase, creatinine, SGPT/ALT, SGOT/AST, GGT, amylase, total bilirubin, conjugated bilirubin as scheduled in Table 1 and Table 2 (Part A), and Table 3 and Table 4 (Part B). In addition, the following parameters will be assessed at baseline and every 6 months of Part B: total cholesterol, triglycerides, HDL and LDL. Abnormal laboratory parameters inconsistent with clinical presentation of MS or suspicious of underlying medical condition should be repeated for accuracy. If an increase of amylase above the clinically notable value (≥ 300 U/L) is observed at any post randomization visit, lipase should be tested to determine the origin of elevated amylase (pancreatic versus extra pancreatic)
- Urinalysis leukocytes, specific gravity, bilirubin, blood, glucose, ketones, pH, protein, and urobilinogen
- The central laboratory will analyze routine blood samples. Blood samples taken at the screening visit are to be in the fasting state. Blood samples taken at subsequent visits are recommended to be in the fasting state. Details regarding collection of samples, shipment of samples, reporting of results, laboratory reference ranges, and alerting abnormal values will be supplied to the site before site initiation in a study laboratory manual. The results of the analysis will be made available to each site by the central laboratory, at the earliest, 48 hours after receipt of the samples by the central laboratory.
- Investigators will be asked to comment on those abnormalities on the respective laboratory result page, including a notation of the clinical significance of each abnormal finding in the patient's source documents. The laboratory sheets will be filed with the patient's source documents. Abnormal laboratory values should not be recorded on the AE eCRF; however, any diagnoses (or signs or symptoms if a diagnosis is not possible) associated with the abnormal findings should be recorded on the AE eCRF.

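### SAP 10.2.2 puts lipids in the screening table, where they are not drawn, and omits eleven collected chemistries from its change-from-Baseline list

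*SAP*

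**What the plan says.** SAP 10.2 opens with a general rule for laboratory data, under which actual values and "change from Baseline values will be presented for clinical laboratory tests with numeric values", by treatment group. It adds shift tables where these are appropriate, with chemistry values flagged low, normal or high.

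SAP 10.2.2 then says which chemistries go into which tables. For screening: "The following laboratory tests will be included for blood chemistry summary tables at the screening visit: sodium, potassium, chloride, calcium, magnesium, phosphate", continuing to "total bilirubin, conjugated bilirubin, total cholesterol, triglycerides, HDL and LDL". For everything after that: "For all other visits, which will be subject to change from Baseline reporting, the tests will include blood urea nitrogen, hemoglobin A1c, albumin", then alkaline phosphatase, creatinine, the liver enzymes, amylase and the two bilirubins. The section also provides a listing of abnormal chemistry values and a table of liver-test elevations.

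On collection, the protocol's Screening Period section ends its chemistry panel without lipids: "total bilirubin, conjugated bilirubin, hemoglobin A1c. Abnormal laboratory parameters inconsistent with clinical presentation of MS". Protocol 11.2.2 gives the lipid schedule: "the following parameters will be assessed at baseline and every 6 months of Part B: total cholesterol, triglycerides, HDL and LDL". The visit sections of protocol 10.3 agree with this; the Month 24 panel, for example, ends with "hemoglobin A1c, and total cholesterol, triglycerides, HDL and LDL".

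The statistical methods for Part B in the protocol synopsis say that safety data will be both listed and summarised by treatment group, and that shift tables and analyses of change from Baseline will be produced.

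**The concern.** The chemistry specification does not match the collection schedule. Lipids are assigned to the one scheduled chemistry visit at which they are not taken and left off the list for the five at which they are. Seven further tests are collected throughout Part B but are not on the list that feeds the change-from-Baseline tables. The SAP gives no reason for either choice.

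A lipid series taken every six months is of use mainly for showing change over time by treatment group. If programming follows 10.2.2 as written, the screening lipid rows will be empty and no change table for lipids is specified. Potassium and magnesium are also affected, and the Part B cardiac exclusion (criterion 7) names low levels of both as examples of added QT risk. A shift in group means that stays within the reference range is the kind of finding most easily missed when only abnormal values are shown.

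**Working it through.** No test statistic or sample size is involved, so the check compares lists.

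**Step 1: count the SAP lists.** The screening list in 10.2.2 has 6 electrolytes and minerals (calcium, chloride, magnesium, phosphate, potassium, sodium), 12 other chemistries (urea nitrogen, random glucose, hemoglobin A1c, albumin, alkaline phosphatase, creatinine, ALT, AST, GGT, amylase, total and conjugated bilirubin) and 4 lipids: 6 + 12 + 4 = 22. The list for other visits keeps the 12 less random glucose: 12 − 1 = 11.

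**Step 2: compare screening.** The protocol screening panel has 6 + 12 = 18 tests. The difference is 22 − 18 = 4, exactly the four lipids.

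**Step 3: compare the later visits.** Collected tests are from protocol 10.3.1 and 10.3.3 to 10.3.10.

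| Part B visits | Collected | On SAP list | Missing | Which |
|---|---|---|---|---|
| Visit 1; Months 6, 12, 18, 24 | 22 | 11 | 11 | 4 lipids, 6 electrolytes and minerals, random glucose |
| Months 3, 9, 15, 21 | 18 | 11 | 7 | 6 electrolytes and minerals, random glucose |

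**Step 4: volume of lipid data.** With about 1200 patients planned (protocol 13.2) and no dropout, the schedule yields at most 1200 × 5 visits × 4 lipids = 24,000 results. Of these, 1200 × 4 × 4 = 19,200 are post-baseline. Dropout lowers both figures.

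**Step 5: does a looser reading remove the problem?** Suppose the screening table was meant to be a Baseline table. Under SAP 5.4.1 the Visit 1 lipids would qualify as Baseline values, so the rows would no longer be empty. The 11-test list would still give lipids no specified post-baseline table.

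**Step 6: which SAP instruction would be followed?** Section 10.2 is general. Sections 10.2.1 to 10.2.3 are specific: hematology names the tests in its change tables, and urinalysis says which tests get summary statistics and which get shift tables. A programmer would reasonably take the explicit 11-test list as the specification for chemistry. The two instructions cannot both be met as written.

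**The case against.** A reader might infer that these eleven tests are never summarised after baseline, or are absent from every post-baseline table. The documents do not support that. The rule in SAP 10.2 covers numeric laboratory tests generally, and its shift-table sentence is not confined to the 11 listed analytes. SAP 10.2.2 lists abnormal chemistry values for all patients. Laboratory changes that the investigator judges clinically significant are recorded as adverse events (protocol 12.6), and these are tabulated. Hemoglobin A1c stays on the change list and urine glucose has a shift table, so glycaemia is partly covered. For QT, ECG values and changes are tabulated directly (SAP 10.4), and protocol 7.2.4 reports a completed thorough-QT study that ruled out a clinically relevant repolarisation effect at 1 mg and 2 mg.

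It can also be said that a shorter list may be deliberate. The retained tests are mostly hepatic and renal, the chemistry groups named in the synopsis, and neither lipids nor electrolytes are adverse events of special interest. No hypothesis tests are run on safety data, and the values are collected whatever the SAP says, so tables could be added later.

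Much of this stands, and it limits the point to a conflict over what will be produced. It does not remove the conflict. Shift tables are conditional, and 10.2.2 names none for chemistry. A listing is not a summary by treatment group and cannot show movement within the normal range. A deliberate reduction would need to be stated and squared with SAP 10.2 and the synopsis. It would also not explain lipids appearing at a visit where they are not drawn.

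**Conclusion.** The point holds as a reporting conflict that should be settled before database lock. SAP 10.2.2 places four lipids at a visit with no scheduled lipid data. Its change-from-Baseline list omits 11 of the 22 tests collected at Visit 1 and Months 6, 12, 18 and 24, and 7 of the 18 collected at Months 3, 9, 15 and 21. That contradicts SAP 10.2 and the synopsis, so by-treatment post-baseline summaries of these tests are not assured; shift tables and the abnormal-value listing cover them only in part. This is an incorrect specification and not merely missing detail, because following it as written yields empty rows and leaves collected tests without a specified change table.

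The counts rest on the panels as printed in the protocol's visit sections. Nothing here affects data collection, the efficacy analyses, sample size, power or type I error.

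**What to change.** In SAP 10.2.2:

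- Remove the four lipids from the screening table, leaving the 18 tests that are collected there.
- Specify actual-value and change-from-Baseline tables for lipids, with Baseline and Months 6, 12, 18 and 24 as the time points.
- Add calcium, chloride, magnesium, phosphate, potassium, sodium and random glucose to the change-from-Baseline list at every visit where they are collected.

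The tables would then carry 22 tests at the five lipid visits and 18 at Months 3, 9, 15 and 21, and 10.2.2 would agree with 10.2. The cost is a change of SAP wording and a few more tables; no additional samples or visits are needed.
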